4.2. Randomization, Stratification, and Blinding

During the entire trial, treatment will be double-blind. Treatment assignments will be based on a computer-generated randomization code provided by Cerevel or designee. Access to the treatment codes will be restricted to personnel charged with generating and maintaining randomization files, packaging IMP, operating the Interactive Response Technology (IRT), and reporting Serious Adverse Events (SAEs) to regulatory agencies. Once a randomization number has been assigned, it must not be reassigned. A participant cannot be randomized more than once in the study.

Randomization will be stratified according to 2 distinct strata:

- Subjects currently using SSRIs or SNRIs during the trial
- Subjects not using SSRIs or SNRIs

The CVL-871 and placebo tablets will be identical in appearance and will be packaged in identically appearing bottles. All subjects will take a single tablet, either CVL-871 or placebo, once daily throughout the Treatment Period. Tablets will be packaged to allow dosage adjustments to be made without breaking the trial blind.

Documentation of breaking the blind should be recorded on the subject's medical record with reason for breaking the blind, the date and time the blind was broken, and the names of the personnel involved. Once the blind is broken for a subject, reinitiation of treatment with IMP cannot occur for that subject.

4.3. Analysis Sets

Participants exposed to IMP before or without being randomized will not be considered randomized, will not be included in any analysis set and will be reported in listings under a study

intervention group named “not randomized but treated”. However, if these participants experienced any safety event, they would be documented separately in the Clinical Study Report (CSR). Participants who are randomized but not treated will not be included in pharmacodynamics (PD), safety, nor pharmacokinetics (PK) analyses. They will only be included in the description of demographic and baseline characteristics. In the tables, they will be part of the treatment group they have been randomized into. In the listings, they will be presented in a “Randomized, not treated” by-line statement, which will be presented prior any other treatment group.

Population	Description	Analysis	Treatment Group
Screened	All subjects who consent to participate in the clinical trial.	NA	NA
Intent-to-Treat (ITT)	All randomized subjects.	Demographic and Baseline Characteristics	Planned
Modified ITT (mITT)	A subset of ITT with randomized subjects who tolerate dose increases to at least Step 4 on Day 21 during titration and have at least 1 post-baseline assessment of the NPI-C apathy subscale score.	Primary analysis set for PD	Planned
Full Analysis Set (FAS)	All randomized subjects who received at least 1 dose of IMP.	Safety analysis	Actual
Pharmacokinetic analysis set (PK set)	All randomized subjects who receive at least 1 dose of IMP and have at least one measurable CVL-871 concentration.	PK analysis	Actual

Abbreviations: IMP=investigational medicinal product; NA=not applicable; NPI-C=Neuropsychiatric Inventory-Clinician; PD=pharmacodynamics; PK=pharmacokinetic.

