The trial is designed as a learning trial instead of a confirmatory trial. The key research question for the pharmacodynamic endpoints will be primarily addressed with an estimand based on the following attributes: 1) treatments as randomized regardless of the final dose level achieved following the titration steps, 2) subjects in the mITT population who reach dose increases to at least Step 4 on Day 21 during titration as the target trial population, 3) change from Baseline to Week 12 as the key time point for assessing change from baseline in measured endpoints of interest, 4) the treatment differences estimated based on the least square mean and the corresponding 80% confidence interval from the MMRM model as the population level summary, and 5) a hypothetical strategy to address intercurrent events (ICEs) of potential death, treatment discontinuations, missed visits, and start of prohibited concomitant medications, unless a treatment-related reason can be identified for a given ICE. As the trial is of exploratory nature, a hypothetical strategy will be used to address the ICEs unless a treatment-related reason can be identified for an ICE. If such reasons are identified, a composite strategy may be taken, eg, assigning highest severity to the case, to ensure appropriate interpretation of the data. Further details, including additional estimands for the research questions on the

[figure not shown]
effect of combined CVL-871 treatment group versus placebo and on the effect of final dose levels of CVL-871 following the completion of titration versus placebo, will be described in the statistical analysis plan.

Safety Review Team:

A Safety Review Team will review the blinded safety data from this trial.

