9.3 Populations for Analyses

For purposes of analysis, the following populations are defined:

Table 7 Populations for Analysis

Population	Description
Enrolled	Comprises all subjects who consent to participate in the clinical trial.
Intent-to-Treat	Comprises all randomized subjects.
Full Analysis Set	Comprises all randomized subjects who receive at least 1 dose of IMP.
Modified ITT Set	Comprises all randomized subjects who receive at least 1 dose of IMP and have at least 1 post-baseline assessment of the NPI apathy subscale score.

Abbreviations: IMP = investigational medicinal product; ITT = intent-to-treat; NPI = Neuropsychiatric Inventory.

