9.4.2 Pharmacodynamic Analyses

Pharmacodynamic endpoints with repeated post-baseline assessments will be analyzed using a mixed-model repeated measures (MMRM) analysis, including baseline score (if applicable), treatment, concomitant SSRI/SNRI use, visit, and the interaction between treatment group and visit as fixed factors in the model. Subject will be included as a random effect in the model.

The trial is designed as a learning trial instead of a confirmatory trial. The key research question for the pharmacodynamic endpoints will be primarily addressed with an estimand based on the following attributes: 1) treatments as randomized regardless of the final dose level achieved following the titration steps, 2) subjects in the modified intent-to-treat (mITT) population who tolerate dose increases to at least Step 4 on Day 21 during titration as the target trial population, 3) change from Baseline to Week 12 as the key endpoint of interest, 4) the treatment differences estimated based on the least square mean and the corresponding 80% confidence interval from the MMRM model as the population level summary, and 5) a hypothetical strategy to address intercurrent events (ICEs) of potential death, treatment discontinuations, missed visits, and start of prohibited concomitant medications unless a treatment-related reason can be identified for a given ICE. If such reasons are identified, a composite strategy may be taken, eg, assigning highest severity to the case, to ensure appropriate interpretation of the data. Further details, including additional estimands for the research questions on the effect of combined CVL-871 treatment group versus placebo and on the effect of final dose levels of CVL-871 following the completion of titration versus placebo, will be described in the SAP.

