11. PHARMACODYNAMICS

The planned timepoints for pharmacodynamic assessments are shown in the Schedule of Assessments (Table 4) which will be completed before the safety assessments and by the same identified caregiver.

All pharmacodynamic endpoints will be analyzed through descriptive statistical methods based on the mITT population. Pharmacodynamic endpoints with repeated post-baseline assessments will also be analyzed, using the mITT population, through statistical inference by using a mixed-model repeated measures (MMRM) analysis, including baseline score (if applicable), treatment, concomitant SSRI/SNRI use, visit (only measured at Visit 5 and 6), and the interaction between treatment group and visit as fixed factors in the model. Subject will be included as a random effect in the model.

An unstructured correlation matrix will be used to model the within-patient errors covariances. The Kenward-Roger approximation will be used to estimate the denominator of degrees of freedom. The least square (LS) mean of each treatment group, difference in the LS mean between the treatment groups, and the corresponding 80% and 95% CI of the differences and p-values will be provided.

If the MMRM model fails to achieve convergence due to complexity of model specification, different covariance structures will be used according to the following order till convergence is achieved:

1. Unstructured correlation (UN)
2. Heterogeneous Toeplitz (TOEPH)
3. Homogeneous Toeplitz (TOEP)
4. First-Order Autoregressive [AR(1)]
5. Compound Symmetry (CS)

The key research questions for the pharmacodynamic endpoints (ie, effect of CVL-871 treatment groups versus placebo) will be primarily addressed with a hypothetical strategy. As such, the missing values will be considered as missing at random (an MMRM analysis assumption).

The primary analysis for all PD endpoints will be performed as described above. However, if the number of subjects with evaluable baseline and post-baseline assessments for a specific PD endpoint is smaller than 15 (all treatment groups combined) or smaller than 2 in any treatment group, only descriptive statistical analyses will be conducted.

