13.2. Impact of COMT (Val-Met) Status

Blood samples will be collected for analysis of catechol-O-methyltransferase (COMT) genotype. Sequencing was performed to detect the c.472G>A, p.Val158Met variant (Chr22:19951271) known familial variant ONLY. There will be one of three following results on the report,

- The variant of interest was NOT detected, corresponding to Val/Val
- The variant of interest was detected; heterozygous, corresponding to Met/Val
- The variant of interest was detected; homozygous, corresponding to Met/Met

The impact of COMT status on safety will be investigated by analysis of TEAEs, presented by primary SOC and PT, showing number and percentage of patients with at least 1 TEAE by COMT status (Met/Met vs Met/Val vs Val/Val) on the FAS.

To evaluate the impact of COMT status on pharmacodynamic, subgroup analyses will be conducted on the following pharmacodynamic endpoints based on the mITT set across the three COMT groups (Met/Met vs Met/Val vs Val/Val):

- NPI-C apathy domain score
- NPI apathy domain score
- DAIR score
- AES-C score

The subgroup analysis will be performed by subgroup rather than including an interaction term.

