14. SUBGROUP ANALYSES

Subgroup analyses of the key pharmacodynamic endpoints, NPI-C apathy score and NPI apathy score will be made based on the mITT set to assess consistency of the intervention effect across the following subgroups:

- Age group (<75, ≥75)
- Sex: female vs. male
- Baseline NPI-C apathy score: ≤baseline median vs. >baseline median (median of the mITT set regardless treatment group)
- Use of concomitant SSRI/SNRI : yes vs. no

Provided that the sample sizes in the subgroups allow, the MMRM analysis method described in [Section 11](#) will be applied to the subgroup analysis. The subgroup analysis will be performed by subgroup rather than including an interaction term. If the number of subjects within a subgroup is too small (less than 9 subgroup overall or less than 1 in any treatment group), only descriptive statistics will be used for the subgroup analysis.

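### No planned PD analysis shows whether the apathy contrasts depend on the post-randomisation Step 4 condition built into the SAP's mITT set

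*SAP*

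**What the plan says.** SAP 4.3 makes mITT the primary PD set and defines it as "A subset of ITT with randomized subjects who tolerate dose increases to at least Step 4 on Day 21 during titration", with at least one post-baseline NPI-C apathy score. Subjects are analysed by planned arm. No second PD set is named: ITT serves baseline description, FAS serves safety, and the PK set serves concentrations.

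SAP 11 states: "All pharmacodynamic endpoints will be analyzed through descriptive statistical methods based on the mITT population". The MMRM also uses mITT. So do the COMT analyses in SAP 13.2 ("subgroup analyses will be conducted on the following pharmacodynamic endpoints based on the mITT set across the three COMT groups") and the subgroups in SAP 14 ("NPI-C apathy score and NPI apathy score will be made based on the mITT set").

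The protocol is not uniform. Table 7 in Protocol 9.3 defines mITT without a Step 4 condition, as randomised subjects who "receive at least 1 dose of IMP and have at least 1 post-baseline assessment of the NPI apathy subscale score". The main PD estimand in Protocol 9.4.2, however, takes mITT subjects "who tolerate dose increases to at least Step 4 on Day 21 during titration as the target trial population"; the synopsis says "who reach dose increases to at least Step 4 on Day 21 during titration as the target trial population". SAP 15 discloses that mITT was modified.

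Under Protocol 4.1.2 (Table 3), Step 4 on Days 17-21 is 2.0 mg in the 3.0 mg arm, an unchanged 1.0 mg in the 1.0 mg arm, and placebo in the placebo arm. Subjects who fail Step 2, the Step 3 rechallenge or Step 4 are discontinued from the trial. Footnote f of the Schedule of Assessments asks for the Visit 6 assessments at early termination (ET); Protocol 7.2.3 asks for that visit if possible.

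**The concern.** Membership of the only PD set is decided by what happens after dosing starts. Through Step 3 both active arms escalate and placebo does not; at Step 4 only the 3.0 mg arm has a real increase. Protocol 2.2.4 names nausea as the most frequent adverse event in both earlier trials. Unequal early loss is therefore plausible, although the documents do not show it.

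If loss differs by arm and tolerability is related to apathy change, the subjects compared are no longer balanced by randomisation, and analysing by planned arm does not restore that. No principal-stratum method is given. The MMRM's missing-at-random assumption covers missing visits within mITT; a subject outside the set contributes nothing.

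Several outputs would reveal unequal loss: set counts by arm, the exclusion listing and reasons for treatment discontinuation (SAP 5.1), TEAEs leading to discontinuation split at Day 21 (SAP 13.1), and PD listings with an mITT flag (SAP 11.1 to 11.3). None estimates a PD contrast. At stake is the reading of the four secondary apathy endpoints, for which SAP 11 reports LS mean differences, 80% and 95% intervals and p-values.

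**Working it through.** **1. The plan's own figures.** With 20% discontinuation, 25 and 20 randomised per arm leave 20 and 16 evaluable. A two-sample noncentral t calculation at two-sided alpha 0.2 gives detectable effects of 0.6784 and 0.7608 for 80% power. The stated 0.678 and 0.761 reproduce. The standard error (SE) of a contrast in SD units is √(2/20) = 0.316 at the planned size. It is √(2/5) = 0.632 at 5 per arm, the 15-subject total below which SAP 11 stops modelling: if numbers are "smaller than 15 (all treatment groups combined) or smaller than 2 in any treatment group, only descriptive statistical analyses will be conducted".

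**2. Model for the shift.** Every input here is an assumption; the documents give no Step 4 exclusion rate, ET completion rate, correlation or slope.

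- Tolerability T and improvement Y are standard normal with correlation ρ.
- The lowest fraction p of T stops before passing Step 4: 20% in an active arm, 5% on placebo.
- A fraction f of those who stop gives an ET score, placed at Week 6.

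Shift in an arm's Week 6 mean (Step 4 set minus the set without that condition):

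ρ × [f·p / (1 − p + f·p)] × [φ(z_p)/(1 − p) + φ(z_p)/p]

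For p = 0.20, φ = 0.280 and the last bracket is 0.350 + 1.400 = 1.750. For p = 0.05, φ = 0.103 and it is 0.109 + 2.063 = 2.171.

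**3. Results.** The Week 6 shift in the contrast at common ρ = 0.5 is 0.5 × (active − placebo); the sign reverses at ρ = −0.5. In a two-visit likelihood analysis with monotone missingness, the Week 12 shift is b times the Week 6 shift, where b is the Week 6-to-12 slope, assumed to be 0.5 to 0.7.

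| f | Active, ρ=1 | Placebo, ρ=1 | Week 6 shift, ρ=0.5 | Week 12 shift | Share of 0.678 |
|---|---|---|---|---|---|
| 25% | 0.1029 | 0.0282 | 0.037 | 0.019-0.026 | 2.8-3.9% |
| 50% | 0.1944 | 0.0557 | 0.069 | 0.035-0.049 | 5.1-7.2% |
| 100% | 0.3499 | 0.1086 | 0.121 | 0.060-0.084 | 8.9-12.5% |

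Against an SE of 0.316, the Week 12 range is 0.06 to 0.27 SE. At the reference trial's SD of 3.2 it is about 0.06 to 0.27 NPI points. The shift is zero if ρ is zero.

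**4. A more extreme case.** With ρ = +0.5 in one arm, −0.5 in the other and every stopper giving an ET score, the Week 6 shift is 0.5 × (0.3499 + 0.1086) = 0.229 SD. At Week 12 it is 0.115 to 0.160 SD.

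**5. Limits of the ET scores.** Step 4 ends on Day 21, so these scores fall at least 43 − 21 = 22 days before the nominal Week 6 visit. The NPI-C and AES-C forms look back 4 weeks (the DAIR, one month). The share of a 28-day look-back before first dose is about (28 − day)/28: 86% for ET on Day 4, 75% on Day 7, 71% on Day 8 and 25% on Day 21.

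**The case against.** The strongest reply is that the restriction is intended. Tolerating Step 4 is an attribute of the protocol's main PD estimand, SAP 15 discloses the changed set, and the trial is a learning trial whose primary objective is safety. That stands, and is why the main set should not change. It does not supply the missing comparison.

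The second reply is that the check may have little power. On the assumed rates with 25 per arm, about 5 subjects in an active arm (25 × 0.20) and 1 on placebo (25 × 0.05) would stop. At 25% to 50% ET completion, roughly one to three early scores are added per active arm. Enrolment also closed before the planned size was reached. This stands too: the result can only be supportive.

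Three stronger readings are tempting, and the documents do not support them:

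- **That SAP 15 removed a check on the Step 4 condition.** The sensitivity analyses dropped there are tied to missing-value handling. The protocol's alternative was a composite strategy for intercurrent events within the Step 4 population. Nothing shows that any dropped analysis varied the Step 4 condition.
- **That the restriction favours CVL-871.** It would if more active subjects are excluded and they would have done worse. The opposite is equally possible.
- **That the distortion is large.** The 0.115 to 0.160 SD case needs opposite-sign correlations between arms and complete ET data. Nothing supports the first, and ET visits are only made if possible.

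**Conclusion.** The gap is real and limited. One set, conditioned on a post-randomisation event that can act differently by arm, carries every post-baseline PD contrast, and no planned analysis shows what that condition does to the four secondary apathy results. Bias is not demonstrated, and neither its direction nor its size can be read from the documents. Under the assumptions above, the Week 12 shift is about 0.02 to 0.08 SD in either direction, at most about a quarter of the planned SE. The primary safety analysis is untouched. The point should be fixed because the check is cheap and mostly uses data already due to be collected, not because the main result is shown to be wrong.

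**What to change.** Keep the Step 4 mITT as the main PD set, then:

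1. **SAP 4.3 and 11.** Add one supplementary MMRM, with the same model and by planned arm, for NPI apathy, NPI-C apathy, DAIR and AES-C. Use all randomised, dosed subjects with at least one post-baseline NPI-C apathy score and no Step 4 condition. Keeping the NPI-C score, rather than the NPI score in Protocol Table 7, means that only the Step 4 condition differs. If the SAP 11 small-number rule applies, present descriptive results only.
2. **ET scores in that analysis.** Place scores from subjects who stop before passing Step 4 at Week 6. SAP 4.4.2 classifies by eCRF label, so a Day 18 score could otherwise enter as Week 12 through the Visit 6/ET label. Classify all other scores as in the main analysis, which is then unchanged; how the main analysis slots ET scores is a separate point.
3. **SAP 5.1.** Tabulate Step 4 exclusions by arm and reason.
4. **Interpretation.** State that the mITT contrast describes subjects who tolerated titration, not all randomised subjects.

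The cost is SAP wording, one extra set of outputs for four endpoints and one table, with no new data collection. The downside is a possibly less favourable second estimate. Few subjects may be added, stoppers without an ET score stay out of both sets, and the added scores are early and partly rate time before first dose. A footnote should say so, and that the result is supportive only.

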4.4. Reporting Conventions

Statistical analysis will be performed using SAS® Version 9.4 or higher.

Standardized and validated SAS macros from PPD will be used to set-up table, listing, figure (TLF) formats (headers/footers and tabulation format) and to tabulate the summaries. All tables and listings will be independently validated using double programming; all figures will be independently validated manually.

4.4.1. Treatment Labels

Table 3: Treatment Order and Labels

Treatment Order	Treatment Group	Treatment Label
1	CVL-871 1.0 mg QD	CVL-871 1.0 mg QD
2	CVL-871 3.0 mg QD	CVL-871 3.0 mg QD
3	Placebo	Placebo
4	CVL-871 Combined	CVL-871 Combined
5	Total	Total

Abbreviations: QD=once daily.

4.4.2. Visit Naming Conventions

The eCRF visit label will be used to classify the assessments.

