4.1.4 Definition of Completed Subject

A subject is considered to have completed the trial if he/she has completed all phases of the trial including the last Treatment Period visit (Visit 6/Week 12), as shown in the Schedule of Assessments in [Section 1.3](#).

A subject who completed all procedures except the Follow-up visit (Visit 7) and Follow-up phone contact would not be considered an early termination subject.

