7.2 Discontinuation of Trial

7.2.1 *Discontinuation of Entire Trial*

If the sponsor terminates or suspends the trial for any reason, prompt notification will be given to investigators, Institutional Review Boards (IRBs)/Independent Ethics Committees (IECs), and regulatory authorities in accordance with regulatory requirements.

7.2.2 *Discontinuation of Individual Site*

Individual trial site participation may be discontinued by the sponsor, the investigator, or the IRB/IEC if judged to be necessary for medical, safety, regulatory, ethical or other reasons consistent with applicable laws, regulations, and Good Clinical Practice (GCP). The investigator will notify the sponsor promptly if the trial is terminated by the investigator or the IRB/IEC at the site.

7.2.3 *Individual Subject Discontinuation From the Trial*

All subjects have the right to withdraw their consent from further participation in the trial at any time without prejudice. Subjects cannot withdraw consent for use of data already collected as part of the trial, but only for future participation. The investigator can also discontinue a subject's participation in the trial at any time if medically necessary.

At the time of discontinuing from the trial, if possible, an early termination visit should be conducted, as shown in the Schedule of Assessments ([Table 1](#)). See the Schedule of Assessments ([Table 1](#)) for data to be collected at the time of trial discontinuation and follow-up and for any further evaluations that need to be completed.

The subject will be permanently discontinued both from the IMP and from the trial at that time.

Complete withdrawal of consent requires a subject's refusal of ALL of the following methods of follow-up:

- Participation in all follow-up procedures specified in the protocol (whether in-clinic, by telephone, or by an in-home visit).
- Participation in a subset of protocol specified follow-up procedures (by a frequency schedule and method, as agreed by subject and staff).
- Contact of the subject by trial personnel, even if only by telephone, to assess current medical condition, and obtain necessary medical or laboratory reports relevant to the trial's objectives.
- Contact of alternative person(s) who have been designated in source records as being available to discuss the subject's medical condition, even if only by telephone, mail, or e-mail (eg, family, spouse, partner, legal representative, friend, neighbor, or physician).

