4.4.3. Visit Windows

Analysis data will be summarized according to the scheduled visit time period for which they were recorded in the eCRF unless otherwise specified.

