4.4.4. Unscheduled Visits

Unscheduled assessments will not be slotted to a particular time point, but will be used when determining the worst-case value. All unscheduled visits will be included in listings.

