PK blood sample ^s			X		X		X			X		
Blood collection for COMT genotyping ^t		X										
Blood samples for future biospecimen research ^u		X										
Other												
IMP dispensing ^v		X	X		X		X					
IMP compliance assessment ^v			X	X	X	X	X	X	X	X		

Abbreviations: AD=Alzheimer’s disease; ADAS-Cog13=Alzheimer’s Disease Assessment Scale – Cognition 13-item scale; AES-C=Apathy Evaluation Scale-Clinician; CaGI-C=Caregiver Global Impression–Change Scale; CaGI-S=Caregiver Global Impression–Severity Scale; COMT=catechol-O-methyltransferase; COVID-19=coronavirus disease-2019; C-SSRS=Columbia-Suicide Severity Rating Scale; DAIR=Dementia Apathy Interview and Rating; DCA=diagnostic criteria for apathy; DLB=dementia with Lewy bodies; ECG=electrocardiogram; eCRF=electronic case report form; ET=early termination; FTD=frontotemporal dementia; HIV=human immunodeficiency virus; IMP=investigational medicinal product; IRT=interactive response technology; mADCS-CGIC=modified Alzheimer’s Disease Cooperative Study-Clinical Global Impression of Change; mCGI-S=modified Clinical Global Impression–Severity Scale; MMSE=Mini-

Mental State Examination; NPI=Neuropsychiatric Inventory; NPI-C=Neuropsychiatric Inventory-Clinician; PK=pharmacokinetic(s); SARS-CoV2=severe acute respiratory syndrome coronavirus 2; VAD=vascular dementia.

- a. Extension of screening may be allowed following discussion and documented approval by the medical monitor prior to the expiration of the Screening Period. Extension will only be granted in rare circumstances and the 30-day duration should be adhered to whenever possible.
- b. Individual sites may require subjects to have SARS-CoV2 testing done prior to randomization. SARS-CoV2 testing may be performed any time after randomization per the investigator's discretion.
- c. Contact with subject via phone call, internet/web, or other acceptable means of communication to check on their status.
- d. Subjects will be monitored during scheduled assessments following dosing and those who do not tolerate the increase to Step 3 dose may decrease back down to Step 2 dose.
- e. Subjects will be monitored during scheduled assessments following dosing and those who do not tolerate the increase to Step 5 dose may decrease back down to Step 4 dose.
- f. The assessments scheduled for Visit 6 are to be performed for any subject who early terminates from the trial.

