- g. Subjects who receive the Step 3 dose increase (rechallenge) on Day 13 will be instructed to call the site on Day 14 (day after they again receive the Step 3 dose) to ensure that they can tolerate the rechallenge.
- h. Informed consent must be obtained before any trial-related procedures are performed.
- i. Assessments will be completed using electronic forms. However, if it is not possible to complete electronic form, then paper forms are permitted.
- j. All responses will be relative to the subject's condition at Visit 2/Baseline, prior to the first dose of IMP.
- k. Full physical and neurological examinations should be completed at Screening and Visit 6/ET. The physical examination should include weight at all time points and height at the Screening Visit only. Physical and/or neurological examinations can be done at any time point during the trial at the investigator's discretion.
- l. At Screening, a triplicate set of 12-lead ECGs is required to assess subject eligibility. A triplicate set of ECGs is 3 consecutive ECGs collected 1 to 2 minutes apart over a 5-minute period. At all other noted time points, a single ECG is required. All ECGs should be performed after the subject has been at rest in a supine/semi-recumbent position for approximately 3 minutes.
- m. Vital sign measurements include blood pressure, heart rate, and body temperature. Duplicate blood pressure and heart rate measurements will be obtained sitting/supine (after 5 minutes of rest) followed by a single standing measurement (after 2 minutes of rising from sitting/supine position). At each visit, body temperature will be obtained once, at the time of the first blood pressure measurement.
- n. The "Baseline/Screening" C-SSRS form will be completed for all subjects at Screening to determine eligibility and the "Since Last Visit" C-SSRS form will be completed at the Baseline Visit to ensure that the subject continues to qualify for the trial. The "Since Last Visit" C-SSRS form will also be completed at all visits after Baseline.
- o. Adverse events (serious and non-serious) and concomitant medications should be recorded from screening through the subject's last visit.
- p. Dipstick urinalysis results are not to be recorded on the eCRFs; any clinically significant abnormality should be captured as an adverse event.
- q. Prolactin results will be partially blinded.

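### Unless the eCRF labels early-termination visits separately, the SAP's label-only visit rule analyses early-termination pharmacodynamic scores as Week 12; the likely bias is small

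*SAP*

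**What the plan says.** SAP 4.4.2 is a single sentence: "The eCRF visit label will be used to classify the assessments". SAP 4.4.3 adds: "Analysis data will be summarized according to the scheduled visit time period for which they were recorded in the eCRF unless otherwise specified". Nothing in SAP 11, 15 or 17.3 specifies otherwise for pharmacodynamic (PD) scores. SAP 4.4.4 says "Unscheduled assessments will not be slotted to a particular time point", but does not say whether an ET visit counts as unscheduled.

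The schedules (Protocol Table 1, SAP Table 4) have one column, Visit 6/ET, at Day 85 and Week 12. Footnote f reads: "The assessments scheduled for Visit 6 are to be performed for any subject who early terminates from the trial". Footnote k uses the same joint name: "Full physical and neurological examinations should be completed at Screening and Visit 6/ET". Protocol 4.1.4 refers to "the last Treatment Period visit (Visit 6/Week 12), as shown in the Schedule of Assessments".

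On timing, Protocol 7.2.3 says: "At the time of discontinuing from the trial, if possible, an early termination visit should be conducted". It continues: "The subject will be permanently discontinued both from the IMP and from the trial at that time". An early terminator therefore has at most one Visit 6 battery, taken on the day of leaving.

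The MMRM in SAP 11 has two post-baseline visits, 5 and 6, and treats missing values as missing at random under a hypothetical strategy. SAP 15 makes that the only approach. Protocol 9.4.2 names change to Week 12 as the key endpoint and lists treatment discontinuation among the intercurrent events handled hypothetically.

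**The concern.** Under the hypothetical strategy, a subject who stops treatment has no Week 12 value, and the model estimates under missing at random what would have been seen. If the ET score carries the Visit 6 label, the Week 12 cell is occupied by a score taken up to nine weeks early and the model has nothing to handle. The reported Week 12 difference is then a mixture of times. If the treatment effect grows over the 12 weeks, the mixture is pulled towards no effect.

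The SAP mITT set requires tolerating dose increases to Step 4 on Day 21, so subjects who fail titration earlier are excluded. The scores at issue run from about Day 22 to the day before the Week 12 window. They would enter the MMRMs for the four secondary apathy scales and the exploratory endpoints modelled the same way, and the descriptive Week 12 summary of ADAS-Cog13.

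**Working it through.** **1. The plan's own figure.** Inputs (SAP 4.1 and 3.1): 25 randomized per arm, 20% discontinuation, two-sided alpha 0.2, power 80%.
- Evaluable per arm: 25 × 0.8 = 20. The detectable effect from the noncentral t is 0.678, as stated.
- For 60 subjects: 20 × 0.8 = 16 per arm gives 0.761, as stated.
- With all 25 per arm counted, the detectable effect would be 0.605, not 0.678.

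The sample size therefore treats those who discontinue as having no Week 12 value. Placing ET scores at Week 12 contradicts that as well.

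**2. How early the scores would be.** Reading the visit window as ±5 days, Week 12 covers Days 80–90, so mis-timed ET scores fall on Days 22–79 (58 days). Spread evenly (assumption), they come on average 85 − 50.5 = 34.5 days before Day 85; the earliest is 63 days before.

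**3. Share of the Week 12 effect kept.** Let p be the share of mITT subjects with an ET score labelled Week 12, and f the mean share of the Week 12 effect present at ET. If ET is unrelated to outcome, kept = 1 − p + p × f.
- Linear to Day 84: f = mean(day/84) = 50.5/84 = 0.601.
- Complete by Day 43: f = mean(min(day/43, 1)) = 0.907.
- Already complete at ET: f = 1.

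| p | Linear to Day 84 | Complete by Day 43 | Complete at ET |
|---|---|---|---|
| 10% | 96% | 99% | 100% |
| 20% | 92% | 98% | 100% |
| 30% | 88% | 97% | 100% |

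The documents give neither p nor f.

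**4. Size in SD units, at the planning effect 0.678 and p = 20%.**
- Linear: 0.678 × 0.20 × (1 − 0.601) = 0.054 SD.
- Complete by Day 43: 0.678 × 0.20 × (1 − 0.907) = 0.013 SD.
- 80% CI half-width, t(0.90, 2n − 2) × √(2/n): 0.368 SD at 25 per arm and 0.595 SD at 10 per arm (an assumed size, since the planned one was not reached).
- The linear loss is 15% and 9% of these half-widths; the Day 43 loss is 3% and 2%.

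**5. Power.** In the linear case, 25 per arm at 0.678 × 0.920 = 0.624 gives 81.8%, against 80.0% with 20 per arm at 0.678. Power is not the problem.

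**6. What study-day assignment does.** Simplified simulation: two visits, no covariates, correlation 0.5, 20% ET unrelated to outcome, linear effect, likelihood estimate using Week 6 to recover missing Week 12.

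| Per arm | Effect kept, before → after | SE (SD units), before → after |
|---|---|---|
| 25 | 92% → 100% | 0.286 → 0.315 (+10%) |
| 10 | 92% → 100% | 0.450 → 0.508 (+13%) |

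Combining bias and SE at 25 per arm, the RMSE before is √(0.286² + 0.054²) = 0.291; after, with almost no bias, it is 0.315. A repeat run with another seed gave 0.288 and 0.311, so the rise is from about 0.29 to about 0.31 SD.

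**The case against.** The strongest objection is that the harm depends on a document not supplied. A shared schedule column with footnote f tells sites which battery to perform; it does not show how the record is labelled. If the eCRF has its own ET label, Week 12 is untouched. If ET is entered as unscheduled, SAP 4.4.4 keeps it out of every time point. Protocol 4.1.4 also separates a subject who completed Visit 6/Week 12 from an early-termination subject, which suggests that the two are thought of as different events. All of this stands, so the point is conditional. A reader might infer that ET scores will certainly be analysed as Week 12; the documents do not show that. But the only visit name they give the ET battery is the joint one, and no SAP rule corrects for it.

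The linear profile is the least favourable of the three. Protocol 4.2 cites effects of another drug at 4 and 6 weeks, which gives no support for growth to Day 84. The 20% is a planning rate for all randomized subjects. Some of those leave during titration and are outside the mITT, and the ET visit is held only where possible. Late ET scores in 20% of the mITT is probably high. This stands too.

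Two other readings are tempting and should not be drawn:
- That placing an ET score at Week 12 breaches the no-imputation statement in SAP 17.3. An ET score is an observed assessment; only its timing is in question.
- That the SAP leaves open whether an ET score admits a subject to the mITT or to the minimum counts in SAP 11. SAP 4.3 asks for one post-baseline NPI-C apathy score and SAP 11 for evaluable post-baseline assessments, neither tied to a visit. Read plainly, an ET score qualifies.

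Finally, the repair makes the estimate less precise and slightly raises its RMSE. That is correct, and it is a cost of the fix.

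**Conclusion.** The point holds as a minor, conditional one. Followed as written, and with a shared eCRF label, SAP 4.4.2 and 4.4.3 place mis-timed scores at the protocol's key time point, contrary to the strategy in SAP 11 and 15. A separate or unscheduled ET label in the eCRF would remove the effect; the SAP does not let a reader tell which applies.

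The likely bias is a loss of 0 to 8% of the Week 12 effect at an assumed 20% ET share, at most 0.054 SD at the planning effect. This rests on evenly spread ET days, ET unrelated to outcome, and the assumed effect profiles. The primary safety objective is not touched.

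**What to change.** Before database lock, add to SAP 4.4.3 a rule such as: *PD assessments at an ET visit are assigned by study day. They count as Week 6 or Week 12 only if they fall in the scheduled window around Day 43 or Day 85 and no scheduled assessment exists in that window. All others are listed, and the visit is left missing in the MMRM and in Week 12 summaries.* If the eCRF already labels ET separately, one sentence saying so is enough.

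The work is one paragraph and one derivation. The statistical cost is fewer nominal Week 12 observations in a trial that closed enrollment early, and a subject whose only post-baseline score is an out-of-window ET score no longer contributes to the MMRM. The gain is freedom from this bias and a match to the stated strategy, not precision. An analysis counting ET scores as Week 12 can be kept as a sensitivity analysis.
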